At each follow-up, participants will complete web-based surveys programmed in Qualtrics by the REC. A link to these computerized surveys will be sent to each participant by the REC and can be completed at the participant's convenience (ideally within 14 days before and 28 days after their scheduled assessment date). Participant VL data will need to be obtained before the study procedures for the respective assessment period is considered complete and the participant is compensated. Data files will be downloaded via Qualtrics by the Data Management Team of the REC. The REC will maintain a linkage of PID and subject name, and these will be stored in password protected files. These web-based surveys will take approximately 60-90 minutes to complete.

Randomization Process/Systems. Participants will be randomized at the end of their baseline assessment into one of two intervention conditions: (1) CPS or (2) SMS. Both intervention conditions will receive 3 months of intervention (i.e., 3 months of CPS or SMS). Each participant's condition will be tracked in REDCap. At the 3-month follow-up, a second stratified randomization will occur in blocks with 8 possible intervention trajectories as follows:

- CPS responders (VL <200 copies/mL) will be randomized to either 9 months of standard care (SC) or 3 months of CPS-T followed by 6 months of SC;
- CPS non-responders (VL \geq 200 copies/mL) will be randomized to 3 months of CPS-I or SMS-I followed by 3 months of CPS-T or SMS-T, respectively, and then 3 months of SC for both groups thereafter;
- SMS responders (VL <200 copies/mL) will be randomized to either 9 months of SC or 3 months of SMS-T followed by 6 months of SC; and
- SMS non-responders (VL \geq 200 copies/mL) will be randomized to 3 months of CPS-I or SMS-I followed by 3 months of CPS-T or SMS-T, respectively, and then 3 months of SC for both groups thereafter.

Participants who are unable to provide a valid HIV VL result at the 3-month time point have approximately 30 days to obtain a HIV VL performed at Quest Diagnostics or have a physician release this information to PRIDE. Participants who are unable to provide this

PROTOCOL TITLE: ATN 144 SMART

information within the timeframe i.e. 30 days after their 3 month follow-up assessment will be treated as non-responders to the intervention and will be re-randomized to an incentive arm. The 30 day window follows the same timeframe as the 30 day window for calls to begin following baseline.

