Quantitative Analysis Plan. The AC's primary analysis will be a comparison of the VL suppression rate (primary outcome) between the CPS and the SMS group at the first stage of randomization (see Study Design). This will be performed using an χ^2 test. We will also compare the drop in VL (measured in logarithmic scale with base 10) between the two groups. Since this is a continuous measure, we will use two-sample t-test to conduct this analysis. We will also compare medication adherence rate (secondary outcome) between the two groups using an χ^2 test. All the primary analyses will be based on initial assignment to groups, using the intention-to-treat (ITT) principle. Each of the primary hypotheses will be tested using linear mixed-effects (LMEs) regression analyses [63]. For testing primary hypothesis 1, the model will include up to 4 repeated assessments of VL suppression (months 0, 3, 6, 12) as the dependent variable. For primary hypothesis 2, we will only focus on non-responders (for both CPS and SMS at stage 1) and compare the VL suppression as dependent variable using a repeated measure LME (months 0, 3, 6, 12). Each LME model will include a random intercept and slope and fixed effects for adherence intervention group, and time, as well as the stratification variables: clinical site, age, gender. A likelihood ratio test will examine the incremental contribution of the group by time interaction, which represents the interaction of interest for Primary Hypothesis 1 and Primary Hypothesis 2, testing for a differential adherence intervention effect over time. The decision rule for each primary hypothesis calls for

PROTOCOL TITLE: ATN 144 SMART

rejection of null hypothesis if this interaction is statistically significant using the Hochberg's step-up alpha adjustment [61]. A site by group interaction will be also examined and included in each model (above) if significant at the .05 level. In addition, likelihood ratio tests will be used to compare the model fit with that having a first order autoregressive (AR1) covariance structure, as described by Hedeker and Gibbons [63].

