1.2 Quantitative Analysis Plan

Original Primary Hypotheses: 1. Youth randomized to CPS will have significantly greater VL suppression (primary outcome) and self-reported medication adherence (secondary outcome) at 24 weeks than those in SMS group. 2. Non-responders randomized to CPS with incentives will have significantly greater VL suppression (primary outcome) and self-reported adherence (secondary outcome) than those randomized to SMS with incentives.

Original Secondary Aims: a) Conduct an exploratory evaluation of tapering the intensity of CPS and SMS (among responders) vs termination after completion of the 24 week intervention to determine if this improves the durability of intervention effects; b) Explore the relative efficacy of the individual intervention sequences embedded within the SMART design for responders and non-responders; and c) Describe moderators of the treatment effect, including demographics, mode of infection, substance use, and mental health. [NOT COMPLETED DUE LOW RENTENTION]

Updated Primary Outcome: Originally, we plan to treat VL suppression as our primary outcome for both co-primary hypothesis. Primary end-point for H1 was at 24 weeks when the proximal outcome was used to determine responder status, while for H2 the Distal outcome was at end of 12 months (or 72 weeks). Due to the difficulty in collecting viral load we proposed to change the primary outcome to a combination of VL suppression and self-reported adherence (SRA). Primary end-points for both co-primary hypothesis is now at 48 week.

Rationale of new definition of Primary Outcome: Since the VLS data may not be available for a significant number of subjects, we plan to use SRA as an additional primary outcome. The usefulness and appropriateness of the usage of these two depends upon the concordance of two measures. To determine that for those subjects we have both VLS and SRA data available, we will first construct a 2×2 contingency table and conduct a chi-square test of association. If they agree on 80% or more cases we will proceed to define (and analyze) the primary outcome as following:

- 1) For any data collection point and randomization event, if VLS data is available it will be used as primary outcome. When VLS data is not available, SRA will be used as primary outcome. This composite definition will be used as primary outcome and will have sufficient power based on hypothesized effect size.

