1.2.1 Primary Analysis Plan

The primary analysis will be a comparison of SRA (primary outcome) between the CPS and the SMS group at the end of first stage of randomization. This will be performed using a χ^2 test. We will also compare the VL suppression between the two groups for those available subjects, albeit this is no longer treated as primary outcome. Since SRA (and VL) is a continuous measure, we will use two-sample t-test to conduct this analysis. We will also compare the self-reported medication adherence rate (secondary outcome) between the two groups using a χ^2 test. All the primary analyses will be based on initial assignment to groups, using the ITT principle. Each of the primary hypotheses will be tested using linear mixed-effects (LME) regression analyses.¹⁰⁴ For testing primary hypothesis 1 (PH1), the model will include up to 3 repeated assessments of VL suppression (weeks 0/baseline, 12, 24, 36, 48). For primary hypothesis 2 (PH2), we will only focus on non-responders (for both CPS and SMS at stage 1) and compare the SRA as dependent variable using a repeated measure LME (weeks 0/baseline, 12, 24, 36, 48). In an effort to get the outcome for PH2 some subject may have final outcome at latter date than 48 weeks. Each LME model will include a random intercept and slope and fixed effects for adherence intervention group, and time, as well as the stratification variables: clinical site, age, gender. A likelihood ratio test will examine the incremental contribution of the group by time interaction, which represents the interaction of interest for PH1 and PH2, testing for a differential adherence intervention effect over time. The decision rule for each primary hypothesis calls for rejection of H_0 if this interaction is statistically significant using the Hochberg adjustment. A site by group interaction will be also examined and included in each model (above) if significant at the 0.05 level. The purpose of the LME based analysis for the primary aim is to determine which of the first-stage intervention, CPS or SMS, is associated with the most improvement in VL and adherence, regardless of which second-stage treatment participants received. Due to contraction of sample size compared to our original plan, we do not plan to adjust α for multiple of testing. In addition to PH1, for those subjects we have VL suppression data available we would perform similar LME to test for its significance. We also expect some subjects with complete VL data and many with partial VL data for

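### The PH2 model runs its group-by-time slope from week 0, although the arms it compares exist only from the second randomisation, so the slope is misspecified and a growing effect is diluted

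*SAP*

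**What the plan says.** SAP 1.2 states PH2 as follows: "Non-responders randomized to CPS with incentives will have significantly greater VL suppression (primary outcome) and self-reported adherence" than those assigned to SMS with incentives. SAP 1.2.1 restricts PH2 to one population, "we will only focus on non-responders (for both CPS and SMS at stage 1"), and will "compare the SRA as dependent variable using a repeated measure LME (weeks 0/baseline, 12, 24, 36, 48"). On model terms it says: "Each LME model will include a random intercept and slope and fixed effects for adherence intervention group, and time". On the test: "A likelihood ratio test will examine the incremental contribution of the group by time interaction". The null hypothesis is rejected on that interaction. The same section says the primary analyses use the initial assignment. SAP 1.2 sets week 48 as the primary end-point for both hypotheses.

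Protocol 16.0 (Quantitative Analysis Plan) has the same structure with VL suppression: "compare the VL suppression as dependent variable using a repeated measure LME (months 0, 3, 6, 12").

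On timing, Protocol 5.0 says: "At the 3-month follow-up, a second stratified randomization will occur in blocks with 8 possible intervention trajectories". Protocol 4.0 (Incentives and Tapering) also sorts participants after three months. Protocol 16.0 (Data Management and Data Quality) and SAP 1.1 instead place the second randomisation after six months. Neither document gives the week-12 value a baseline role, puts a knot at re-randomisation, or constrains the arms to be equal before it.

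**The concern.** The CPS-I and SMS-I arms come into being at the second randomisation. Before it, the expected difference between them is zero. On the month-3 schedule, two of the five SAP visits (and two of the four Protocol visits) fall in that period. A random intercept and slope with a time effect is most naturally read as linear time. The tested quantity is then one straight-line divergence that starts at week 0, at a randomisation PH2 does not test. That line cannot describe a difference that is zero up to week 12 and starts afterwards.

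At stake are the meaning of the PH2 estimate and some power for a co-primary hypothesis that rests on about half the sample. The reference to initial assignment adds to the problem: read literally, it makes the PH2 group variable the stage-1 arm rather than the arm PH2 names.

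**Working it through.** **Plan's own figure.** SAP 1.2.4 claims at least 80% power at 60 per group, effect size 0.55, two-sided 0.05, 10% attrition. With 54 per group, a two-sample t-test has 80.8%, so the figure reproduces. It concerns the stage-1 comparison. Protocol 16.0 assumes about 50% responders, which leaves 120 × 0.5 / 2 × 0.9 = 27 per arm for PH2.

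**Inputs.** 27 per arm; SRA scaled to SD 1; maximum difference 0.55 SD; within-person correlation ρ = 0.4 (Protocol 16.0 gives 0.3 to 0.5); visits t = 0, 1, 2, 3, 4; second randomisation at t = 1 (month 3). Effect shape and random-slope variance are assumptions, as the documents give neither. Arm differences d at the five visits:
- step: 0, 0, 0.55, 0.55, 0.55
- ramp: 0, 0, 0.183, 0.367, 0.55
- late: 0, 0, 0, 0.275, 0.55

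**Planned slope.** Centred times are −2, −1, 0, 1, 2, with sum of squares 10. The estimate is Σ(t − 2)d / 10:
- step: (0.55 + 1.10)/10 = 0.165
- ramp: (0.367 + 1.10)/10 = 0.147; the true rate is 0.55/3 = 0.183, and 0.147/0.183 = 0.80
- late: (0.275 + 1.10)/10 = 0.1375

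Without slope variance, SE = √[(2/27)(1 − ρ)/10] = √[(2/27)(0.06)] = 0.0667.

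**Anchored slope.** Weeks 0 and 12 are kept with no arm difference, and x = (0, 0, 1, 2, 3). With c = ρ/(1 + 4ρ) = 0.154, the estimate is [Σxd − cΣxΣd] / [Σx² − c(Σx)²]. The denominator is 14 − 0.154 × 36 = 8.46.
- step: (3.3 − 1.523)/8.46 = 0.210
- ramp: 0.183, the true rate
- late: (2.2 − 0.762)/8.46 = 0.170

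SE = √[(2/27)(0.6)/8.46] = 0.0725.

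**Power**, Φ(estimate/SE − 1.96), with the same calculation repeated after adding slope variance of 0.5 SD² by week 48:

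| Shape | Planned vs anchored, no slope variance | Planned vs anchored, slope variance 0.5 |
|---|---|---|
| step | 70% vs 83% | 52% vs 57% |
| ramp | 59% vs 72% | 43% vs 50% |
| late | 54% vs 65% | 39% vs 46% |

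**Waning effect** (0.55, 0.41, 0.28 SD at weeks 24, 36, 48). Without slope variance: 30% vs 41%. With slope variance 1.0 the order reverses, 17% vs 15%. At the extreme corner of ρ = 0.5 and slope variance 1.0, the same calculation gives 18% vs 15% for waning and 44% vs 42% for step.

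**If re-randomisation is after six months.** Weeks 0, 12 and 24 would all precede it. The late shape is then the steady-growth case: the planned slope of 0.1375 compares with a true 0.275 per visit, so it is halved.

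**The case against.** Several stronger readings are tempting, and the documents do not support them.

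- *The early visits weaken the test and should go.* They do not. Cutting week 0 from the linear test lowers power from about 60% to 49% (ramp) and from 70% to 42% (step). Used as baseline, both visits add precision.
- *The test is invalid.* Randomisation balances pre-randomisation values in expectation, so type I error is not inflated.
- *The early visits cost some 20 points of power.* At 30 per arm, ρ = 0.4 and a step effect, the planned slope has 74% and the mean of weeks 24 to 48, adjusted for weeks 0 and 12, has 94%. That gap reflects a change of estimand to a three-visit mean. An adjusted contrast at the stated week-48 end-point has 68%, and for a late effect the mean does worse than the planned slope (42% vs 58%).
- *The taper-versus-termination model has the same fault.* SAP 1.2.2 gives no visits or time origin for it, so none can be shown.

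Two objections stand. If time were fitted as categorical, the attenuation from linearity would not arise; the SAP does not say so, and its random slope points to linear time. And the power gain depends on an unknown effect shape: it shrinks with slope variance and can turn into a small loss.

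**Conclusion.** The point holds as a misspecified, unanchored interaction. Assuming linear time and re-randomisation at month 3, a steadily growing PH2 effect is underestimated by 20%. Anchoring raises power by 11 to 13 points for step, ramp and late effects with no slope variance, and by 5 to 7 points with 0.5 SD². For waning effects with large slope variance it gains little or loses about 2 points, nearly 4 at the extreme corner. All power figures rest on 27 per arm, ρ = 0.4 unless stated, and the assumed shapes. This is a matter of estimand and efficiency, not of false-positive control. It merits a change because PH2 is co-primary and the change needs no new data.

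**What to change.** First reconcile Protocol 4.0 and 5.0 with Protocol 16.0 and SAP 1.1 on when the second randomisation takes place. Then, in SAP 1.2.1:

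1. Define the PH2 group as the second-stage assignment and limit the initial-assignment wording to PH1.
2. Treat all values up to re-randomisation as baseline, either as covariates or as outcomes constrained to no arm difference.
3. Start the group effect at re-randomisation and state whether time is linear or categorical.
4. Pre-specify the post-randomisation contrast, consistent with the week-48 end-point.

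Step 4 involves a trade-off. An anchored straight line overstates the week-48 difference if the effect is a step (3 × 0.210 = 0.63 against 0.55 SD). A week-48 contrast with categorical visits avoids that. In the constrained model its SE is 0.239 (27 per arm, ρ = 0.4, no slope variance), so power is Φ(0.55/0.239 − 1.96) = 63% for any of the three shapes. That is below the planned slope for a step and above it for ramp and late effects.

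The cost is SAP wording. A missing week-12 value has to be imputed if it is a covariate; the constrained model handles it directly under the SAP's existing ignorable-attrition assumption.

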Sample Size and Power. Statistical power analyses examined the sample size requirements to detect greater than chance group differences on primary outcome (Primary Hypotheses 1 and 2). Because two primary hypotheses have been proposed, the Hochberg alpha adjustment will be used in hypothesis testing. The smaller of those sequential alpha-levels of $.025 (=0.05/2)$ was used in our estimates of the multiplicity-adjusted sample sizes. Preliminary data have traditionally been used for this purpose, but the small sample of the pilot data to provide estimates that are too imprecise for sample size calculations [70]. The power analyses examined the sample sizes required to detect clinically meaningful group differences in the VL suppression rate over time (i.e., the slope). Statistical power was estimated in a Monte-Carlo simulation study using SAS PROC MIXED over 1000 iterations. This represents the differential course for the two interventions over time. Based on the results, the protocol requires recruitment of 190 participants ($\approx 95/\text{group}$ at 1st stage) with $\approx 50\%$ non-responder in 2nd stage. The power table above shows the statistical power to detect standardized interaction effects of various magnitudes (0.45 to 0.55) for the Ns and a two-tailed alpha-level of 0.025. The intra-class correlation coefficient within subjects varied (ICC: .30, .40, .50, based on pilot data). The sample size of 95/group provides sufficient statistical power to detect differences in slopes that results in endpoint differences of $.45 \text{ sd. units}$ with $\text{ICC}=.30$ or .40 and 0.50. In the power analysis it is assumed about 50% responder state at the end of stage 1, thus resulting about 95 subjects in responder and non-responder group.

Strategies for Attrition. Attrition introduces bias and reduces power, precision and generalizability [71]. In keeping with the Intent-to-Treat principle we distinguish between intervention and study termination (complete withdrawal). Accordingly, we will make every effort to continue assessments for the entire course of randomized intervention,

PROTOCOL TITLE: ATN 144 SMART

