1.1 Data Management and Data Quality

The first randomization involves allocation to CPS vs. SMS using a 1:1 allocation ratio. This step will use stratified randomization in permuted blocks to achieve balance in distribution of behaviorally and perinatally infected youth. The REC data team will program the randomizer in Qualtrics and will not participate either in the intervention delivery or in the adherence reinforcement steps. The protocol team will monitor race, ethnicity, and gender to ensure balanced distribution at the first stage. After 6 months, stratified randomization will occur with permuted blocks within each trajectory. Since second stage randomization is dependent on first stage response status, we will only maintain the balance within each first stage treatment outcome when randomizing at the second stage.

Following the Analytic Core's (AC) standard quality assurance, including checking for outliers and abnormal values using graphical methods, we will verify that the distributions of measures meet the assumptions of the statistical tests to be used, applying a formal test such as the Shapiro-Wilk's test [60]. Transformations will be used when distributional assumptions are not fulfilled. Tests will be conducted to identify potential relationships among baseline demographic and clinical variables and our dependent variables and to see whether they are balanced between groups. If a baseline variable is not balanced between groups and is correlated with the dependent variable ($r > .30$), we will include this variable as a covariate in subsequent analyses. Since we will test more than one primary hypothesis with one primary outcome variable (VL suppression), the Hochberg step-up multiplicity adjustment will be used with a two-tailed family wise alpha-level of .05 [61]. All other tests described below will each have a two-tailed alpha-level of 0.05. Outcome analyses will be based on the principle of intention-to-treat [62].

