1.2.4 Sample Size and Power

Sample Size and Power. Statistical power analyses examined the sample size requirements to detect greater than chance group differences on primary outcome (PH1 and Ph2). We have used Susan's formula with a total sample size of 120.

<http://people.seas.harvard.edu/~samurphy/papers/APPProof.pdf>

| Power Table | | | |
|--------------------|------------|------------|-----------------------------|
| ES | p | N | N(10% attrition adjustment) |
| 0.55 | 0.4 | 86 | 96 |
| | 0.5 | 104 | 116 |
| | 0.6 | 130 | 144 |
| | 0.7 | 174 | 192 |
| 0.6 | 0.4 | 74 | 80 |
| | 0.5 | 88 | 98 |
| | 0.6 | 110 | 120 |
| | 0.7 | 146 | 160 |

Alternatively, for the two groups comparison this corresponds to n=60/group. This sample size is sufficient to provide 80% power (or more) for a standardized Effect Size (ES) of 0.55 or more, using a t-distribution for a two tailed test with $\alpha=0.05$, with 10% attrition assuming equal responder rate (p) in both arms.

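### The PH1 mixed model estimates a week-0 CPS–SMS difference that randomisation makes zero in expectation; sharing one week-0 mean would gain power in the deciding test at no cost

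*SAP*

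**What the plan says.** For PH1, SAP 1.2.1 states that "the model will include up to 3 repeated assessments of VL suppression (weeks 0/baseline, 12, 24, 36, 48". Week 0 is therefore part of the response, not a covariate. The same section says "Each LME model will include a random intercept and slope and fixed effects for adherence intervention group, and time", then "A likelihood ratio test will examine the incremental contribution of the group by time interaction", and finally "The decision rule for each primary hypothesis calls for rejection of H_0 if this interaction is statistically significant". Protocol section 16.0 (Quantitative Analysis Plan) has the same structure, with months 0, 3, 6 and 12.

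Protocol section 5.0 fixes the order of events: "Participants will be randomized at the end of their baseline assessment into one of two intervention conditions". SAP 1.1 adds that "The first randomization involves allocation to CPS vs. SMS using a 1:1 allocation ratio".

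Neither document sets the week-0 arm means equal. The only rule about baseline, in SAP 1.1, adds a covariate if it is both imbalanced and correlated with the outcome above .30. That rule leaves the group main effect in the model.

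**The concern.** When time is coded from 0, the group main effect in a model with group, time and group-by-time is the arm difference at week 0. Baseline is measured before allocation, so any observed difference there is chance. The model nevertheless estimates it from the data, and the slope contrast has to be estimated alongside it. Information in the baseline values that could sharpen the treatment comparison goes unused.

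Only precision is at stake, but it is the precision of the one test that decides PH1, in a trial whose target fell from 190 (protocol section 16.0) to 120 (SAP 1.2.4). The baseline values needed to recover it are already being collected.

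**Working it through.** **Inputs**
- Per arm: SAP 1.2.4 says "Alternatively, for the two groups comparison this corresponds to n=60/group". Less 10% attrition, 60 × 0.9 = 54.
- Effect 0.55 SD and two-sided alpha 0.05: SAP 1.2.4.
- Visits t = 0, 1, 2, 3, 4 (weeks 0 to 48): SAP 1.2.1.
- ICC ρ: protocol section 16.0, "The intra-class correlation coefficient within subjects varied (ICC: .30, .40, .50, based on pilot data". These values were written for the 190-participant plan; the SAP gives none.
- Linear divergence from zero: protocol section 16.0 powers on slope differences reaching an endpoint difference. Slope difference = 0.55/4 = 0.1375 per visit.
- Random-slope SD, s: not stated. I assume a range, in baseline SD units per visit, with the slope independent of the intercept and the effect held at 0.55 baseline SD.

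**The plan's own figure.** A two-sample comparison with 54 per arm and effect 0.55 has noncentrality 0.55 × √27 = 2.86. Power is 80.8% by the noncentral t, which reproduces the stated 80%. That figure is for a two-group t-test, not for the interaction that decides PH1.

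**Variance of the slope difference.** With complete data:

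Var = (2/54) × [(1 − ρ)/I + s²]

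- Week-0 difference free: I = Σ(t − 2)² = 10.
- Week-0 difference set to zero: I = Σt² − ρ(Σt)²/(1 + 4ρ) = 30 − 100ρ/(1 + 4ρ) = 16.4, 14.6, 13.3 for ρ = .30, .40, .50.

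**No random-slope variance (s = 0)**

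| ICC | SE free | SE shared | z free | z shared | Power free | Power shared | Gain (points) |
|---|---|---|---|---|---|---|---|
| .30 | 0.0509 | 0.0398 | 2.70 | 3.45 | 77.0% | 93.2% | 16.2 |
| .40 | 0.0471 | 0.0390 | 2.92 | 3.53 | 83.1% | 94.1% | 11.1 |
| .50 | 0.0430 | 0.0373 | 3.20 | 3.69 | 89.2% | 95.8% | 6.7 |

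The variance falls by 39%, 32% and 25% (1 − 10/I). Likelihood-ratio simulations with 400 runs each gave 74% against 92% at ICC .30 and 90% against 95% at ICC .50, with Monte Carlo error of about 2 points.

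**With a random slope**, power at ICC .30/.40/.50. The last column is the implied week-48 variance relative to baseline, 1 + 16s².

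| s per visit | Free | Shared | Gain (points) | Variance ratio |
|---|---|---|---|---|
| 0.1 | 71/77/83% | 88/89/91% | 8–16 | 1.16 |
| 0.2 | 58/62/66% | 70/71/73% | 7–12 | 1.64 |
| 0.25 | 50/53/57% | 60/60/62% | 5–9 | 2.00 |
| 0.35 | 37/39/41% | 42/42/43% | 3–5 | 2.96 |

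**Effect complete by week 12, then flat** (differences 0, .55, .55, .55, .55). The free fit gives slope (−1 + 0 + 1 + 2) × 0.55/10 = 0.11 and week-0 term 0.44 − 2 × 0.11 = 0.22, so the baseline term takes 0.22/0.55 = 40% of the effect. With s = 0, power is 58/65/72% free and 97/96/96% shared.

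**Time coded as visits, contrast at week 48** (s = 0). The contrast variance is (2/54) × 2(1 − ρ) free and (2/54) × (1 − ρ²) shared. Power is 68/74/82% and 85/88/91%.

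**Type I error of the shared-mean test.** Null simulations that kept the random intercept and slope stayed at 4.8–5.8%, including restricted and binary baselines. Dropping the random slope gave about 9–10% for binary outcomes.

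**The case against.** The planned model is conventional and valid, and the documents do not contradict themselves in using it. That stands. A reader might infer bias or an inflated type I error in the planned test. Nothing supports that: the point is one of efficiency.

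A reader might also quote 7–16 points as the loss. That range sets to zero a random-slope variance that the plan explicitly includes, and the gain shrinks as the variance grows. It may be tempting to add that the plan misses its 80% promise. With s = 0, the test as written exceeds 80% at two of the three ICCs, and the promise was made for a different comparison. The larger shortfalls depend on slope SDs that the documents do not give.

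Two other strong readings fail. For an early effect that then stays flat, the baseline term takes 40% of it, not most. And the likeness to a change-score analysis is exact only for a baseline-to-visit contrast; for a linear slope it is an analogy.

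The inputs are also a loose fit. The ICCs were given for viral suppression, no document gives one for self-reported adherence (SRA), and entry criteria restrict the week-0 outcome. A check on binary suppression, with everyone unsuppressed at week 0, linear divergence and assumed rates, still showed a loss of about 10–16 points. SAP 1.2.1 is further unsettled on the PH1 outcome, the number of visits and alpha. Those passages need reconciling before any power figure is final, but no reading of them removes the free week-0 term.

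**Conclusion.** The point holds as a free improvement. The PH1 model estimates a week-0 arm difference that is zero in expectation by design, and the deciding test gives up power as a result. For a continuous outcome with linear divergence and complete data on 54 per arm, sharing the week-0 mean gains about 7–16 points over the protocol's ICC range with no random-slope variance. The gain falls to 3–5 points at a slope SD of 0.35 per visit, where the outcome variance nearly triples by week 48. It is larger if the effect is complete by week 12 and then flat. That pattern is plausible, since first-stage contact lasts three months, but it is only one scenario.

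The direction is the same in every case computed; the size depends on a slope variance that the plan does not state. The conclusion is confined to PH1. For PH2, non-responders are re-randomised at 3 months, so weeks 0 and 12 both precede that allocation and this constraint does not carry over as written.

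**What to change.** In SAP 1.2.1, and to match in protocol section 16.0, for PH1 only:

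- Keep week 0 in the outcome vector and remove the group main effect, so that both arms share one week-0 mean (constrained longitudinal data analysis). Test the group-by-time term after baseline. If time is coded as visits, set the week-0 means equal and test the group-by-visit contrast at the chosen endpoint.
- Keep the planned random intercept and slope, or use an unstructured covariance. State this explicitly, because a random-intercept-only version can inflate type I error when entry criteria restrict the baseline outcome.
- Report the model with a free week-0 difference as a sensitivity analysis.

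The cost is a sentence or two of wording and one model term, with no new data or participants. The change relies on every week-0 value being obtained before allocation. The protocol's sequence already provides for this, and it can be confirmed from collection dates.
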